Appendix II Study Procedures and Assessments

Study Procedures and Assessments

Visit Name	Screening	Baseline^e + IMP	Phone Contact ^k	Phone Contact ^k	Primary Outcome + IMP	Phone Contact ^k	Phone Contact ^k	dMI	Phone Contact ^k	Phone Contact ^k	dMI	Phone Contact ^k	Phone Contact ^k	dWI	Phone Contact ^k	Phone Contact ^k	IMP	Phone Contact ^k	Phone Contact ^k	Completion	Withdrawal ^v
	P	lace	ebo-	cont	rolle	ed P	erio	d]	Exte	nsio	n Pe	erioo	ł				
Visit Number	1	2	3	4	5	6	7	8 z	9 z	10 z	11 z	12	13	14	15	16	17	18	19	20	
End of Week ^a	-4	0	4	8	12	16	20	24	28	32	36	40	44	48	52	56	60	64	68	72	
Visit Window ^b (days relative to nominal visit)	-2		-2	±2	±2	±2	±2	±2	±2	±2	±2	±2	±2	±2	±2	±2	±2	±2	±2	+2	+2
Screening and Baselin	e Pr	oce	dure	es an	d A	sses	smei	nts													
Signed informed consents	\checkmark																				
Demographics (age, sex, race)	\checkmark																				
Diagnosis	\checkmark																				
Documented evidence of previous failure of 2-4 migraine preventive medications ^c	\checkmark																				
Disease-specific history	\checkmark																				
Relevant history (social, medical, psychiatric, neurological)	\checkmark																				
Recent medication	\checkmark	\checkmark																			
Smoking, alcohol consumption	\checkmark																				
Height	\checkmark		ļ	 	 							ļ			 	 	 	 			
Blood sampling for serology (HIV, HBsAg, anti-HCV)	\checkmark																				

Table 1Study Procedures and Assessments

Visit Name	Screening	Baseline ^e + IMP	Phone Contact ^k	Phone Contact ^k	Primary Outcome + IMP	Phone Contact ^k	Phone Contact ^k	IMP	Phone Contact ^k	Phone Contact ^k	IMP	Phone Contact ^k	Phone Contact ^k	IMP	Phone Contact ^k	Phone Contact ^k	IMP	Phone Contact ^k	Phone Contact ^k	Completion	Withdrawal
	P	lace	bo-o	cont	rolle	d P	erio	d				I	Exte	nsio	n Pe	erioo	1				
Visit Number	1	2	3	4	5	6	7	8 z	9 z	10 z	11 z	12	13	14	15	16	17	18	19	20	
End of Week ^a	-4	0	4	8	12	16	20	24	28	32	36	40	44	48	52	56	60	64	68	72	
Visit Window ^b (days relative to nominal visit)	-2		-2	±2	±2	±2	±2	±2	±2	±2	±2	±2	±2	±2	±2	±2	±2	±2	±2	+2	+2
Blood sampling for other screening (e.g., β-hCG, FSH)	1																				
Inclusion/exclusion criteria	1	√f																			
Signs and symptoms present at Screening and/or Baseline (before IMP intake) (recorded on an Adverse Event Form)	V	V																			
Randomization		√d																			
Efficacy Assessments	PR	Os) ^g						·			ı						·				
eDiary daily																					v
recording ^h eDiary data review and compliance check		1	1	1	1	V	1	1	1	1	1	1	1	1	1	1	1	1	1	1	√*
PGIC			√¹		1			1			1			1		 	1			1	√v
MBS		√			1			\checkmark			1			V	L	L	1			V	√⊻
Pharmacoeconomic A	ssess	sme	nts (PRO																	
HIT-6		1	1	1	1	1	1	1	V	1	1	1	1	1	1	1	1	1	1	1	√ ^v
MSQ v2.1		1	,	,	1	,	1	1	,		1	,	,	1	,		1	,	,	1	√ ^v
EQ-5D-5L		1	1	1	1	1	1	1		1	1	1	1	1	1	1	1	1	1	1	√v
HCRU		V	1	1	1	1	1	1	1	1	1	1	1	1	1	1	1	1	1	N	√v
WPAI		\checkmark	V	\checkmark	\checkmark	V	1	\checkmark	N	V	1	1	\checkmark	V	\checkmark	\checkmark	1	V	\checkmark	٧	√v
Safety Assessments Adverse events		√ m,n	V	V	√ m,n	V	٧	√ m,n	1	V	√ m,n	√	1	√ m,n	٧	1	√ m,n	1	1	1	1

Visit Name	Screening	Baseline ^e + IMP	Phone Contact ^k	Phone Contact ^k	Primary Outcome + IMP	Phone Contact ^k	Phone Contact ^k	IMP	Phone Contact ^k	Phone Contact ^k	IMP	Phone Contact ^k	Phone Contact ^k	IMP	Phone Contact ^k	Phone Contact ^k	IMP	Phone Contact ^k	Phone Contact ^k	Completion	Withdrawal ^v
	P	lace	bo-	cont	rolle	ed P	erio	d]	Exte	nsio	n Po	erioo	ł				
Visit Number	1	2	3	4	5	6	7	8 z	9 z	10 z	11 z	12	13	14	15	16	17	18	19	20	
End of Week ^a	-4	0	4	8	12	16	20	24	28	32	36	40	44	48	52	56	60	64	68	72	
Visit Window ^b (days relative to nominal visit)	-2		-2	±2	±2	±2	±2	±2	±2	±2	±2	±2	±2	±2	±2	±2	±2	±2	±2	+2	+2
Blood and urine sampling for clinical safety laboratory tests	\checkmark	\sqrt{n}			\sqrt{n}			\sqrt{n}			\sqrt{n}			\sqrt{n}			\sqrt{n}			V	\checkmark
Blood ADA		\sqrt{n}			\sqrt{n}			\sqrt{n}			\sqrt{n}			\sqrt{n}			\sqrt{n}			\sqrt{p}	
Vital signs body temperature including, weight, ECGs	\checkmark	\sqrt{n}			\sqrt{n}			\sqrt{n}			\sqrt{n}			\sqrt{n}			\sqrt{n}			V	\checkmark
Physical Examination		\sqrt{n}			\sqrt{n}			\sqrt{n}			\sqrt{n}			\sqrt{n}			\sqrt{n}				
C-SSRS°								\checkmark			\checkmark			\checkmark	[[[[\checkmark	\checkmark
Biobanking																					
Blood sampling for gene expression profiling (RNA) ^w		\sqrt{n}			\sqrt{n}			\sqrt{n}						\sqrt{n}						V	V
Blood sampling for metabolomics/ proteomics (plasma) ^w		\sqrt{n}			\sqrt{n}			\sqrt{n}						\sqrt{n}						\checkmark	\checkmark
Blood sampling for pharmacogenetics (DNA) – optional ^x		\sqrt{n}																			
Blood sampling for possible future ADA assessment ^y								\sqrt{n}												\checkmark	\checkmark
Other Study Procedur	es a	nd A	Asse	ssm	ents																
IMP administered ^r		\sqrt{q}			\sqrt{q}			\sqrt{q}			\sqrt{q}			\sqrt{q}			\sqrt{q}		[[
IMP accountability ^s																				[
Concomitant medication (prescription and non- prescription)		\checkmark	\checkmark	V	\checkmark	\checkmark	\checkmark	\checkmark	\checkmark	\checkmark	\checkmark	V	V	\checkmark	V	\checkmark	\checkmark	V	\checkmark	1	\checkmark
eDiary training ⁱ	\checkmark								 					 	 						

Visit Name	Screening	Baseline ^e + IMP	Phone Contact ^k	Phone Contact ^k	Primary Outcome + IMP	Phone Contact ^k	Phone Contact ^k	IMP	Phone Contact ^k	Phone Contact ^k	IMP	Phone Contact ^k	Phone Contact ^k	IMP	Phone Contact ^k	Phone Contact ^k	IMP	Phone Contact ^k	Phone Contact ^k	Completion	Withdrawal ^v
	P	Place	ebo-	cont	rolle	ed P	erio	d]	Exte	nsio	n Pe	erio	d				
Visit Number	1	2	3	4	5	6	7	8 z	9 z	10 z	11 z	12	13	14	15	16	17	18	19	20	
End of Week ^a	-4	0	4	8	12	16	20	24	28	32	36	40	44	48	52	56	60	64	68	72	
Visit Window ^b (days relative to nominal visit)	-2		-2	±2	±2	±2	±2	±2	±2	±2	±2	±2	±2	±2	±2	±2	±2	±2	±2	+2	+2
PRO training ⁱ	\checkmark																				
eDiary closeout ^j																				\checkmark	\checkmark
Pregnancy test	\sqrt{t}																\checkmark			\checkmark	\checkmark
Exit Interview								\sqrt{u}													\sqrt{u}

ADA = anti-drug antibody; C-SSRS = Columbia-Suicide Severity Rating Scale; ECG = electrocardiogram; EQ-5D-5L = Euroqol 5 Dimensions; HBsAg = hepatitis B surface antigen; FSH = follicle-stimulating hormone; HCRU = Health Care Resource Utilization; β hCG = beta-human chorionic gonadotropin; HCV = hepatitis C virus; HIT-6 = Headache Impact Test; HIV = human immunodeficiency virus; IMP = investigational medicinal product; MBS = Most Bothersome Symptom; MSQ v2.1 = Migraine-Specific Quality of Life Questionnaire Version 2.1; PGIC = Patient Global Impression of Change; PRO = patient-reported outcome; WPAI = Work Productivity and Activity Impairment questionnaire

- a All assessments (except for the requirement of screening assessments prior to the Baseline Visit) may be completed over a maximum of 2 consecutive days with the exception of PROs (see footnote g below); if so, the first day is considered the "visit" day according to the schedule.
- b If the date of a clinic visit or phone contact does not conform to the schedule, subsequent visits should be planned to maintain the visit schedule relative to the Baseline Visit.
- c The patients must have documented evidence of failure in the past 10 years of 2-4 different pharmacological migraine preventive medications. Acceptable documentation of previous treatment failures includes medical or pharmacy record or physician's confirmation specific to each treatment.
- d Randomization will occur at the Baseline Visit 28-30 days after the Screening Visit and after eligibility criteria are confirmed by the investigator.
- e Dosing must occur at the Baseline Visit.
- f Inclusion and exclusion criteria review must be done prior to dosing at the Baseline Visit.
- g Assessments involving interviews and scales must be done before the infusions. All efficacy and pharmacoeconomic assessments are PROs. PROs which are scheduled in alignment with a clinic visit can be completed in the clinic or in the remote setting within 3 days prior to the scheduled clinic visit date. Additionally, PGIC (at Week 4 only), HIT-6, EQ-5D-5L, HCRU, WPAI which are scheduled in alignment with a phone contact must be completed in the remote setting and can be completed on the day or within 3 days prior to the scheduled phone contact date.
- h The eDiary assessments will be completed in the remote setting on a daily basis.

- i At the Screening Visit, the patient must be assisted with the provisioning and training of the eDiary and training of efficacy and pharmacoeconomic assessments (PROs). Details will be provided in a separate user manual.
- j The eDiary closeout will take place at the Completion/Withdrawal Visit, while the patient is at site. Details will be provided in a separate user manual.
- k The patients will be contacted via phone every 4 weeks between infusion visits for eDiary data review and compliance check, to ensure that selected assessments have been completed and for collection of relevant information such as AEs and concomitant medication.
- 1 PGIC at Week 4 must be completed in the remote setting.
- m At infusion visits, IRRs must be checked as part of the overall AE collection, after infusion and before the patient is discharged from the site.
- n At infusion visits, physical examination, ECG, blood sampling (for clinical safety laboratory tests, ADA and biobank) and urine samples (for clinical safety laboratory tests and pregnancy) must be conducted before infusion. AEs, vital signs including body temperature should be checked before and after infusion.
- o The C-SSRS will be administered by the authorized rater at the clinic and prior to infusion.
- p Patients who test positive for ADA at the Completion will be asked to provide up to two additional blood samples for immunogenicity testing at 12-week intervals for up to 24 weeks.
- q At infusion visits, patients must be monitored for a period of 1 hour from the end-of-infusion. Patients will be requested to stay longer should the investigator determine this is clinically warranted.
- r An unblinded pharmacist or designee is responsible for receiving, storing and preparing IMP. The pharmacist or designee will not be responsible for other aspects of the clinical trial where blinding is necessary.
- s A designated unblinded CRA is responsible for the IMP accountability.
- t Pregnancy test at Screening to be conducted using serum β-HCG and at all other visits using urine testing.
- u *Exit Interview subset*: Patients undergoing the exit interviews must provide signed subset-specific Informed Consent. The exit interview will be conducted at the Week 24 Visit or at the Withdrawal Visit for patients withdrawing prior to Week 24. The exit interview must be conducted after all visit assessments are completed. Details will be provided in a separate exit interview guide.
- v Patients who withdraw, except for those who withdraw their consent, will be asked to attend a Withdrawal Visit 12 weeks after the last dose of IMP and undergo Safety Follow-Up evaluations. Patients who withdraw prior to Week 24 will undergo additional Efficacy Follow-Up evaluations.
- w Exploratory gene expression profiling (RNA) and metabolomics/proteomics are an integrated part of the study and are covered by the main Informed Consent.
- x Sampling for pharmacogenetics is optional and a separate signed Informed Consent must be in place to cover this analysis.
- y Whole blood samples for serum separation and potential future ADA analyses will be drawn at the Baseline Visit and at Week 24.
- z If a decision is made to end enrolment early, patients who have not yet completed their Week 12 Visit will immediately transfer to the Extension Period. Patients originally randomized to placebo will be scheduled for Visit 8 immediately and active treatment will be initiated. Patients originally randomized to eptinezumab will be scheduled for Visit 9 or 10 or 11. For these patients, the scheduling of Visit 9 or 10 or 11 should allow for the next dose of IMP to be received at Visit 11, that is 12 weeks after their first dose. Patients who have already completed their Week 12 Visit will continue to finalise 24 weeks of treatment in the Placebo-controlled Period and enter the Extension Period at Visit 8. Patients must continue to complete the daily headache eDiary during the transfer to the Extension Period.

Appendix III PDS Migraine Event Definition

PDS Migraine Event Definition

The PDS definition of a migraine day, which was used at randomization for the classification into EM and CM stratum as defined in inclusion criterion 10, is a day with a migraine event defined as:

Table 2PDS Migraine Event Definition

6.1.6	Migraine Event Definition	3.3.2	Any reported headache (Duration \geq 30 minutes) that meets all 3 of the following criteria:
			1. Duration:
			a. \geq 4 hours
			OR
			b. \geq 30 minutes AND < 4 hours AND subject took medication because they believed they were experiencing a migraine.
			2. Had at least 2 of the following
			a. Unilateral location
			b. Pulsating quality
			c. Moderate or Severe pain intensity
			d. Aggravation by or causing avoidance of routine physical activity
			3. Had at least 1 of the following
			a. Nausea
			b. Vomiting
			c. Photophobia AND Phonophobia

See PDS for details regarding the definitions and calculations used for eligibility.

Appendix IV SAS[®] Code

SAS[®] Code

Primary Analysis

The SAS[®] code for the primary analysis of the primary endpoint described in Section 12.3.2 is given below. Here, it is assumed that the ordering of the levels of the treatment factor is: 100 mg, 300 mg, placebo.

```
proc mixed data = xxxx method = REML;
class USUBJID TRTP(ref = 'Placebo') STRATUM COUNTRY AVISITN;
model CHG = BASE TRTP AVISITN STRATUM COUNTRY BASE*AVISITN
STRATUM*AVISITN TRTP*AVISITN / DDFM = KR;
repeated AVISITN / subject = USUBJID type = UN;
lsmestimate TRTP*AVISITN "100 mg vs. Placebo, Weeks 1-12"
[1, 1 1] [1, 1 2] [1, 1 3] [-1, 3 1] [-1, 3 2] [-1, 3 3]/
divisor = 3 cl;
lsmestimate TRTP*AVISITN "300 mg vs. Placebo, Weeks 1-12"
[1, 2 1] [1, 2 2] [1, 2 3] [-1, 3 1] [-1, 3 2] [-1, 3 3]/
divisor = 3 cl;
```

run;

Key Secondary Analysis

The SAS[®] code for conducting the key secondary analyses described in Section 12.4.2 is given below. Note that p-values to be included in the test strategy will be computed from a likelihood ratio test.

run;

Secondary Analysis

The SAS[®] code for computing p-values from the extended CMH test for the secondary endpoints described in Section 12.5 is given below. The p-values are computed separately for each active treatment group. In the code below the relevant p-value is stored in the p_value output data set.

```
proc freq data = xxxx (where = (TRTP in ('EPTI xxx mg' 'PBO') and AVISIT =
'xxxx'));
    output out = p_value CMHRMS;
```

```
tables STRATUM*TRTP*AVAL / cmh2;
run;
```

Sensitivity Analysis (placebo-based Multiple Imputation)

The SAS[®] code that will be the basis for the placebo-based multiple imputation (pMI) sensitivity analysis for the key secondary endpoint, HIT-6, mentioned in Section 12.4.4, is given below. Note that data transformation steps are omitted and only the most crucial parts are shown.

The procedure for the pMI method will include the following steps:

- 1. Impute missing intermittent data using Markov Chain Monte Carlo (MCMC) methodology by treatment group with the model for HIT-6 total score at baseline and at Week 4, 8, 12, 16, 20, and 24, using PROC MI from SAS[®], with seed = 101990 and 200 imputations, to impute data to a monotone missing data pattern under a MAR assumption.
- 2. At time t, perform pMI according to the placebo-treated patients, where the monotone missing values are assumed to follow an MNAR pattern. Only observations up to time t will be included for the placebo group. Based on the model established using only placebo data, observations up to but not beyond time t-1 in the eptinezumab treatment groups will be used for imputing the missing data at time t. The regression model will include stratum and observed or imputed outcomes up to time t (including the baseline scores), and will use the MONOTON REG option in PROC MI with seed = 88775.
- 3. Assemble a dataset containing data for all patients, including the imputed data from time t, to serve as predictors for the imputation of the next visit.
- 4. Repeat steps 2 to 3 sequentially over all visits (t+1, t+2...).
- 5. Analyse the 200 complete datasets using the same MMRM model as described in Section 12.4.2.
- 6. Combine the estimated treatment effects obtained across the imputed datasets using PROC MIANALYZE from SAS[®].

In the below, it is assumed that:

transposed_data: transposed analysis data with each AVISITN as a separate variable mono data: data with monotone missing data pattern

imputed data: data with missing values imputed

mmrm_data: data with CHG calculated from imputed values and with additional variables to be used in the modelling added

diff_data: data with estimated treatment differences from the converged models fit on each of the 200 datasets

results data: data with the combined estimated treatment effects

Code parts:

*Impute intermittent missing values;

```
proc mi data = transposed_data out = mono_data nimpute = 200 seed = 101990;
  by TRTP;
   var BASE AVISITN 3 AVISITN 4 AVISITN 5 AVISITN 6 AVISITN 7 AVISITN 8;
  mcmc chain = multiple
   impute = monotone;
run;
*Impute monotone missing values;
proc mi data = mono data seed = 88775 nimpute = 1 out = imputed data;
   by IMPUTATION ;
   class STRATUM TRTP;
   monotone regression;
   mnar model (AVISITN 3 AVISITN 4 AVISITN 5 AVISITN 6 AVISITN 7 AVISITN 8 /
        modelobs = (TRTP = "PBO"));
   var stratum base avisitn 3 avisitn 4 avisitn 5 avisitn 6 avisitn 7
       AVISITN 8;
run;
*Execute model on imputed data;
ods output lsmeans = LS01 diffs = D01 ConvergenceStatus = CONV01;
proc mixed data = mmrm data method = REML;
   by _IMPUTATION_;
   class AVISITN COUNTRY STRATUM TRTP USUBJID;
   model CHG = BASE TRTP AVISITN STRATUM COUNTRY BASE*AVISITN
               STRATUM*AVISITN TRTP*AVISITN / DDFM = KR;
   lsmeans TRTP*AVISITN / diff cl alpha = 0.05;
   repeated AVISITN / subject = USUBJID type = un;
run;
*Combine model estimates;
proc mianalyze parms(classvar = full) = diff data;
      by AVISITN;
       class TRTP;
       modeleffects TRTP*AVISITN;
       ods output ParameterEstimates = results_data;
run;
```

Appendix V PCS Criteria

PCS Criteria

Laboratory Test	CDISC Term	Unit	PCS Low	PCS High
Haematology / Coagulation				
B-haemoglobin	HGB	g/L	\leq 95 (women)	\geq 165 (women)
			\leq 115 (men)	\geq 185 (men)
B-erythrocytes (red cell count)	RBC	x 10E12/L	\leq 3.5 (women)	\geq 6.0 (women)
			\leq 3.8 (men)	\geq 7.0 (men)
B-haematocrit (packed cell volume)	НСТ	V/V	\leq 0.32 (women)	\geq 0.50 (women)
			\leq 0.37 (men)	\geq 0.55 (men)
B-MCV (mean cell volume)	MCV	fL	\leq 0.8 x LLN	\geq 1.2 x ULN
B-total leucocyte (white cell count)	WBC	x 10E9/L	≤2.8	≥16
B-neutrophils/leucocytes	NEUTLE	%	≤ 20	≥ 85
B-eosinophils/leucocytes	EOSLE	%		≥ 10
B-basophils/leucocytes	BASOLE	%		≥ 10
B-lymphocytes/leucocytes	LYMLE	%	≤ 10	\geq 75
B-monocytes/leucocytes	MONOLE	%		≥15
B-thrombocytes (platelet count)	PLAT	x 10E9/L	≤ 75	≥ 600
P-INR (prothrombin ratio)	INR	Ratio		≥ 2.0
B-prothrombin time	PT	Sec		≥ 18
Liver				
S-aspartate aminotransferase	AST	U/L		\geq 3 × ULN
S-alanine aminotransferase	ALT	U/L		\geq 3 × ULN
S-bilirubin	BILI	µmol/L		\geq 34
S-bilirubin, direct	BILDIR	µmol/L		≥12
S-bilirubin, indirect	BILIND	µmol/L		\geq 22
S-alkaline phosphatase	ALP	U/L		\geq 3 × ULN
S-gamma glutamyl transferase	GGT	U/L		\geq 200
S-alpha-glutathione S-transferase (alpha-GST)	GSTAL	µg/L		≥20
Kidney				
S-creatinine	CREAT	µmol/L		$\geq 1.5 \text{ x ULN}$
B-urea nitrogen (BUN)	BUN	mmol/L		≥ 11
S-uric acid (urate)	URATE	µmol/L		\geq 510 (women)
				\geq 630 (men)
Electrolytes				
S-sodium (natrium)	SODIUM	mmol/L	≤ 125	≥155
S-potassium (kalium)	Κ	mmol/L	≤ 3.0	≥ 6.0

Table 3 PCS Criteria for Clinical Safety Laboratory Tests

Laboratory Test	CDISC Term	Unit	PCS Low	PCS High
S-calcium	CA	mmol/L	≤ 1.8	≥ 3.0
S-chloride	CL	mmol/L	≤ 1.8 ≤ 90	≥ 3.0 ≥ 117
S-magnesium	MG	mmol/L	≤ 90 ≤ 0.6	≥ 1.7 ≥ 1.3
S-phosphate (phosphorus,	PHOS	mmol/L	≤ 0.65	≥ 1.3 ≥ 1.95
(inorganic)	rnos	IIIII01/L	≤ 0.05	≥ 1.95
S-bicarbonate	BICARB	mmol/L	≤ 12	≥ 38
Endocrine / Metabolic				
B-glucose, non-fasting/unknown	GLUC	mmol/L	≤ 3.4	≥9.4
B-glucose, fasting	GLUC	mmol/L	≤ 3.0	≥ 6.0
S-glucose, non-fasting/unknown	GLUC	mmol/L	\leq 3.9	≥ 11.1
S-glucose, fasting	GLUC	mmol/L	≤ 3.5	≥ 7.0
B-glycosylated haemoglobin, fasting	HBA1C	Hb fract.		≥ 0.065
S-prolactin	PROLCTN	mIU/L		≥ 1350
S-thyrotropin/TSH	TSH	mIU/L	≤ 0.3	≥ 5.5
S-protein (total)	PROT	g/L	\leq 45	≥95
S-albumin	ALB	g/L	≤ 27	
Lipids				
S-cholesterol total, non- fasting/unknown	CHOL	mmol/L		≥ 7.8
S-cholesterol total, fasting	CHOL	mmol/L		≥ 6.2
S-triglycerides, non- fasting/unknown	TRIG	mmol/L		≥ 5.65
S-triglycerides, fasting	TRIG	mmol/L		\geq 4.2
S-LDL cholesterol, non- fasting/unknown	LDL	mmol/L		≥ 5.3
S-LDL cholesterol, fasting	LDL	mmol/L		\geq 4.9
S-HDL cholesterol, non- fasting/unknown	HDL	mmol/L	≤ 0.8	
S-HDL cholesterol, fasting	HDL	mmol/L	≤ 0.9	
Cardiac/Skeletal/Muscle				
S-creatine kinase (total)	CK	U/L		\geq 400 (women) \geq 750 (men)
S-creatine kinase MB isoenzyme	CKMB	μg/L		$\geq 8.5 \text{ or}$
5	CKMBCK	%		\geq 3.5% of total CK
S-lactate dehydrogenase (total)	LDH	IU/L		≥ 750
S-troponin I	TROPONI	µg/L		≥ 1.5
S-troponin T	TROPONT	μg/L		≥ 0.4
Infection		-		
S-C-reactive protein	CRP	mg/L		≥25
S-globulin (total)	GLOBUL	g/L	≤15	≥ 55

Laboratory Test	CDISC Term	Unit	PCS Low	PCS High
Urine				
Urinary pH	PH		\leq 4	≥ 9

Table 4 PCS Criteria for Vital Signs, Weight/BMI, and Waist Circumference

Variable	CDISC Term	Unit	PCS Low	PCS High
Waist circumference	WSTCIR	Cm	decrease $\geq 7\%$	increase $\geq 7\%$
Weight	WEIGHT	Kg	decrease $\geq 7\%$	increase $\geq 7\%$
Body Mass Index	BMI	kg/m2	decrease $\geq 7\%$	increase $\geq 7\%$
Pulse rate, supine/sitting/unknown	PULSE	beats/min	< 50 and decrease ≥ 15	\geq 120 and increase \geq 15
Diastolic blood pressure, supine/sitting/unknown	DIABP	mmHg	≤ 50 and decrease ≥ 15	\geq 105 and increase \geq 15
Systolic blood pressure, supine/sitting/unknown	SYSBP	mmHg	\leq 90 and decrease \geq 20	\geq 180 and increase \geq 20
Orthostatic systolic blood pressure	OBP	mmHg	≤ -30	
Orthostatic pulse rate	OPR	beats/min		≥ 20
Temperature	TEMP	°C	decrease ≥ 2	\geq 38.3 and increase \geq 2

Increase/decrease is relative to the baseline value.

Table 5PCS Criteria for ECG Parameters

ECG Parameter	CDISC Term	Unit	PCS Low	PCS High
Absolute Time Interval				
PR interval	PRAG	Msec		≥ 260
QRS interval	QRSAG	Msec		≥ 150
QT interval	QTAG	Msec		\geq 500
Derived Time Interval				
Heart rate	EGHRMN	beats/min	< 50 and decrease ≥ 15	\geq 120 and increase \geq 15
QTcB interval	QTCBAG	Msec	< 300	> 500 or increase > 60
QTcF interval	QTCFAG	Msec	< 300	> 500 or increase > 60

Increase/decrease is relative to the baseline value.

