8.5 IMP Visits (Visits 2, 5, 8, 11, 14, 17)

At the IMP Visits, the infusion is preceded by assessments of vital signs including body temperature, concomitant medications, AEs, physical examination, ECG, blood and urine sampling and C-SSRS administration.

Assessments involving interviews and scales must be administered before the infusion. PROs will be completed in the clinic the following order; HIT-6, PGIC, MBS, MSQ v2.1, EQ-5D-5L, HCRU, WPAI. Alternatively, PROs which are scheduled in alignment with an IMP visit can be completed in the remote setting within 3 days prior to the scheduled clinic visit date.

Patients must complete the daily eDiary entries prior to infusion. A compliance check of the eDiary will be conducted and the patient must be assisted with re-training if necessary. See section 9.2.2 for further details on eDiary.

Patients will be monitored for at least 1 hour following end-of-infusion and before being discharged from the clinic. Patients will be requested to stay longer should the investigator determine this is clinically warranted. After the infusion, the patients will be under observation, but not confined to bed, unless the investigator decides, based on the patient's condition, that it is in the best interest of the patient to be confined to bed. Vital signs including body temperature, infusion related reactions (IRRs) and AEs will be checked after infusion and before the patient is discharged from the site. AEs should be collected prior to assessment of IRRs.

Exit Interview subset: The exit interview will be conducted at Visit 8 (Week 24 Visit or at the Withdrawal Visit for patients who withdraw prior to Week 24). The exit interview must be conducted after all visit assessments are completed. A visit window of 2 weeks is allowed for the exit interview from the last assessment conducted for Visit 8/Withdrawal Visit (for patients who withdraw prior to Week 24). See section 9.5.1 for further details on the exit interview.

8.6 Phone Contacts (Visits 3, 4, 6, 7, 9, 10, 12, 13, 15, 16, 18, 19)

The patient will be contacted via phone every 4 weeks between infusion visits for eDiary compliance check, to ensure that selected assessments have been completed and for collection of relevant information such as AEs and concomitant medication.

A compliance check of the eDiary will be conducted and the patient must be assisted with retraining if necessary. See section 9.2.2 for further details on eDiary.

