9.4.3 Vital Signs

The investigator may appoint a designee (for example, nurse or paramedic) to measure vital signs including body temperature, provided this is permitted according to local regulations and provided the investigator has trained the designee how to measure these. The investigator must take responsibility for reviewing the findings.

Pulse rate and blood pressure will be measured using a standard digital meter. Pulse rate and blood pressure will be measured in the following order: supine, sitting, and standing after the patient has rested in each position for at least 3 minutes. Pulse rate will be recorded before each blood pressure measurement.

Vital signs including body temperature must be assessed prior to blood sampling.

Any out-of-range values considered clinically significant by the investigator must be recorded as an adverse event on an *Adverse Event Form*.

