4.2 Definition of Baseline

For migraine and headache endpoints, the baseline value will be based upon the data recorded in the headache eDiary during the first 28 days following screening.

For other endpoints, the baseline assessment will be the latest available valid measurement taken prior to the administration of IMP.

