13.2 General Methodology for Other Safety Data

Unless otherwise specified, tables, graphs, and listings will be based on the APTS for the Placebo-controlled Period and APTS_LT for the Extension Period.

All tables and graphs will be presented by treatment group for the Placebo-controlled Period and by treatment sequence group for the Extension Period.

The denominators for the summaries of a given variable will be based on the number of patients with non-missing values at a given visit or during the assessment period.

Descriptive statistics for the safety variables, both absolute values and changes from baseline, will be presented by visit, separately for each period.

The number and percentage of patients with at least one PCS value at any post-baseline assessment time point will be summarized by variable, separately for each period. All available assessments in each period will be included in the evaluation of PCS values.

For patients with post-baseline PCS values in the Placebo-controlled Period, listings will be provided including all the values for those patients for the variable prior to entering the Extension Period, with flagging of PCS values and out-of-reference-range values for inclusion in the *CSR*.

For patients with PCS values occurring after start of V8 IMP infusion, similar listings will be provided including all the values for those patients for the variable for inclusion in the *addendum to CSR*.

For inclusion in the *CSR*, all the adverse events occurring before entering the Extension Period in patients with post-baseline PCS values in the Placebo-controlled Period will be listed by treatment group and patient screening number; the listing will include the PCS value, the assessment date, the change from baseline in PCS value, the preferred term for the adverse event, and start date and stop date of the adverse event. The PCS values and adverse events will be listed in chronological order according to assessment date and the start date of the adverse event.

Similar listings will be provided for patients with PCS values occurring after start of V8 IMP infusion, including all the adverse events for the patients, for inclusion in the *addendum to CSR*.

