13.4 Vital Signs and Weight

The PCS criteria used for vital signs and weight are the Lundbeck standard PCS criteria described in SOP_09978: *GPV – PCS and standard reference values for laboratory investigations, vital signs and ECGs in clinical studies*, version 6, and are also included in Table 4.

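### SAP Table 4 flags a high temperature only if it is at least 38.3 °C and at least 2 °C above baseline, so above a baseline of 36.3 °C the working limit is baseline + 2 °C and the PCS count may understate raised temperatures

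*SAP*

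**What the plan says.** The PCS-high entry for temperature in SAP Appendix V, Table 4 is a level of at least 38.3 °C joined by *and* to a change of at least 2 °C ("38.3 and increase"). The table's footnote fixes the reference for the change: "Increase/decrease is relative to the baseline value". For endpoints not taken from the eDiary, SAP 4.2 states that "the baseline assessment will be the latest available valid measurement taken prior to the administration of IMP".

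SAP 13.4 gives the source: "The PCS criteria used for vital signs and weight are the Lundbeck standard PCS criteria", taken from a named SOP and reproduced in Table 4.

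Temperature is measured around each infusion. SAP Appendix II, Table 1, footnote n reads "AEs, vital signs including body temperature should be checked before and after infusion", and Protocol 8.5 adds "Vital signs including body temperature, infusion related reactions (IRRs) and AEs will be checked after infusion", before the patient leaves the site. Under SAP 13.2, "All available assessments in each period will be included in the evaluation of PCS values". That section builds the count of patients with at least one PCS value from these flags, separately for each period, together with the value listings and the linked adverse event listings.

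**The concern.** A reader of the PCS table will take 38.3 °C as the temperature limit that was applied. When a level and a change must both be met, the stricter of the two governs, and here that depends on where the patient starts. A patient at 36.8 °C who reaches 38.5 °C after an infusion is above the printed level but has risen by only 1.7 °C, so no flag is set.

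The PCS rule is the only fixed numerical criterion in the plan that turns temperature readings into numbers of patients per arm, and it triggers the patient listings. If it is less sensitive than it looks, the PCS table can understate how many patients had a raised temperature after an intravenous antibody infusion. No efficacy endpoint, test or error rate is affected.

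**Working it through.** **Inputs.** Level 38.3 °C, change 2 °C, joined by *and* (SAP Table 4). The change is measured from baseline (Table 4 footnote), and baseline is the last valid value before IMP (SAP 4.2). The documents do not give the distribution of baseline temperature, so it is assumed below.

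**Working limit.** A reading T is flagged when T ≥ 38.3 and T − baseline ≥ 2, that is, when T ≥ max(38.3, baseline + 2). The two parts coincide at a baseline of 38.3 − 2 = 36.3 °C. At or below 36.3 °C the limit is exactly 38.3 °C. Above it, the limit is baseline + 2.

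| Baseline (°C) | Working limit (°C) | Excess over 38.3 | Rise at a reading of 38.3 |
|---|---|---|---|
| 36.0 | 38.3 | 0.0 | 2.3 |
| 36.3 | 38.3 | 0.0 | 2.0 |
| 36.5 | 38.5 | 0.2 | 1.8 |
| 36.6 | 38.6 | 0.3 | 1.7 |
| 36.8 | 38.8 | 0.5 | 1.5 |
| 37.0 | 39.0 | 0.7 | 1.3 |

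The unflagged band runs from 38.3 °C up to, but not including, baseline + 2.

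**Share of patients affected (assumption).** With baseline normal with mean m and SD s, the share with a limit above 38.3 °C is P(baseline > 36.3) = 1 − Φ((36.3 − m)/s). For m = 36.2 and s = 0.3 this is 1 − Φ(0.33) = 36.9%. For m = 36.8 and s = 0.3 it is 1 − Φ(−1.67) = 95.2%.

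| Assumed mean (°C) | SD 0.3 | SD 0.4 | SD 0.5 |
|---|---|---|---|
| 36.2 | 36.9% | 40.1% | 42.1% |
| 36.3 | 50.0% | 50.0% | 50.0% |
| 36.4 | 63.1% | 59.9% | 57.9% |
| 36.5 | 74.8% | 69.1% | 65.5% |
| 36.6 | 84.1% | 77.3% | 72.6% |
| 36.8 | 95.2% | 89.4% | 84.1% |

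**How far above 38.3 °C.** The share with a limit of at least 38.5 °C (baseline of 36.5 °C or more) is 16% to 27% at mean 36.2, 50% at mean 36.5, and 73% to 84% at mean 36.8. The share with a limit of at least 38.8 °C is 2% to 12% at mean 36.2, 25% to 35% at mean 36.6, and 50% at mean 36.8.

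**Other two-part rows of Table 4.** On the high side, the printed level governs for most plausible baselines: systolic up to 180 − 20 = 160 mmHg, diastolic up to 105 − 15 = 90 mmHg, pulse up to 120 − 15 = 105 beats/min. On the low side, the change part takes over as it does for temperature: systolic below 90 + 20 = 110, diastolic below 50 + 15 = 65, pulse below about 50 + 15 = 65.

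**The case against.** The strongest reply is that the rule is declared and looks deliberate. SAP 13.4 names it as the sponsor's standard. The same appendix uses *or* where either part should suffice, as in the QTcF row (above 500 msec or an increase above 60 msec), so the *and* is unlikely to be a misprint. The low-side pulse and blood pressure rows also tighten with baseline, so a change part that overrides the level is not peculiar to temperature. This stands. A reader might infer that the temperature row is an anomaly, or that the 2 came from an unfinished Fahrenheit conversion. The documents support neither: the row is in °C, Fahrenheit appears nowhere, and the SOP is not available to check.

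The second reply is that other routes remain. SAP 13.2 summarises absolute values and changes by visit, SAP Section 6 includes the maximum, and the vital-sign visit windows in SAP 19.2.2 separate pre-dose from post-dose. Protocol 9.4.3 adds "Any out-of-range values considered clinically significant by the investigator must be recorded as an adverse event on an" Adverse Event Form, and SAP 13.1.6 tabulates treatment-emergent events on dosing days. This stands in part. A by-visit maximum shows the highest reading in an arm, not how many patients had a raised one. The adverse event route depends on the investigator's judgement, and the infusion-related groups in SAP Table 6 name no body-temperature group.

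The third reply is that the rule is descriptive and identical in every arm. That is correct and limits the weight of the point.

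**Conclusion.** The point holds as a limited loss of sensitivity in one descriptive safety output. That both parts are required, and that 38.3 °C has no effect above a baseline of 36.3 °C, follows from the SAP text alone. How many patients this touches does not: the range of roughly 37% to 95% rests on an assumed normal baseline with mean 36.2 to 36.8 °C and SD 0.3 to 0.5 °C.

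A reader might go further and conclude that the limit is well above 38.3 °C for most patients, or that post-infusion fevers go unreported. The documents do not show this. Most patients are affected only if the median baseline exceeds 36.3 °C. The excess is 0.2 to 0.3 °C at baselines of 36.5 to 36.6 °C, and a majority reach a limit of 38.8 °C or more only if the median is at least 36.8 °C. Readings at or above the working limit are flagged, and those in the unflagged band still enter the by-visit summaries and, where judged clinically significant, the adverse event data. Nor is the PCS result wrong by the plan's own definition. It may simply count fewer patients than the printed 38.3 °C suggests. This is a cheap improvement, not a serious defect.

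**What to change.** Keep the company-standard temperature row in Table 4 and have the sponsor confirm that *and* with 2 °C is intended. Add to the outputs in SAP 13.4 one descriptive line giving the number and percentage of patients with any post-baseline temperature of 38.3 °C or more regardless of change, by treatment group and period, using the grouping conventions of SAP 13.2, with a listing of those patients. This uses the sponsor's own level and readings already collected, and needs no new threshold. The cost is one extra summary line and a few more listed values.
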